5.0 Outcome Measures

5.1 Primary Outcome

5.1.1 The primary outcome will be feasibility. The data gathered will be used to inform the development of a larger future study. Feasibility

in this study will be defined as follows: the proportion of patients who agree to participate in the intervention. Among patients who agree to participate the proportion that are able to complete the intervention and document barriers to participation.

5.1.2 For all patients – both in the active and control groups, we will determine the proportion who are able to have the baseline and follow-up assessments of measures of interest (cardiovascular imaging, exercise measures (peak VO₂ and 6 min walk distance).

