6.0 Analytic Plan

We will enroll 21 patients with 14 in the PAI and 7 in HLI. The goal of this study is to determine feasibility and preliminary efficacy data. We now describe these measurements.

Feasibility:

We will determine the proportion of patients who agree to participate in the intervention. Next, among patients who agree to participate we will determine what proportion are able to complete the intervention and document barriers to participation. For all patients – both in the active and control groups, we will determine the proportion who are able to have the baseline and follow-up assessments of measures of interest (cardiovascular imaging, exercise measures (peak VO₂ and 6 min walk distance).

In addition, for the patients receiving the active intervention we will assess the change in outcomes of interest to determine preliminary efficacy estimates. The control patients will also provide some preliminary efficacy assessments.

With 21 patients we can estimate a 95% exact confidence interval (using the Clopper-Pearson method) for the proportion of patients who have measurements taken with a width of 0.578 (i.e., from 0.211 to 0.789 if the observed proportion is 0.5 – most conservative assumption).

For estimating the outcomes of interest, a 95% confidence interval will extend +/- 0.769 standard deviation if there are 8 patients in the active group, +/- 0.635 if the sample size is 12 and +/- 0.554 SDs if the sample size is 15.

A number of assessments will be made on the patients enrolled. These include measures of peak exercise cardiac output, calculated A-V O₂ difference and VO₂, and pre- exercise measures of LV & cognitive function, HRQOL, six-minute walk distance (6minWD) and fatigue. For each of these measures we will calculate descriptive statistics in order to get some preliminary data concerning the mean values and variability of these measures. We will also obtain mean and variability values of the MRI cardiac function and HRQOL data from the 47 lymphoma patients in the parent study that did not undergo the two arms of the intervention as noted in this pilot addendum. This information will be helpful for designing a future clinical trial.

Improving Exercise Capacity with a Tailored Physical Activity Intervention in Lymphoma and Breast Cancer Patients Undergoing Treatment – An addendum to NIH
R01CA167821 “Early Imaging Detection of CV Injury after Cancer”
Wake Forest Baptist Comprehensive Cancer Center
CCWFU# 99112

Accrual:

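### The 95% confidence half-width of 0.769 SD does not belong to 8 patients: 8 gives 0.836 SD, and 0.769 SD is the value for 9

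*Combined protocol and SAP*

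**What the plan says.** Section 6.0 sets the enrolment: "We will enroll 21 patients with 14 in the PAI and 7 in HLI". For the continuous outcomes it says that "for the patients receiving the active intervention we will assess the change in outcomes of interest to determine preliminary efficacy estimates", and adds that "The control patients will also provide some preliminary efficacy assessments".

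One sentence then gives the expected precision at three sample sizes. The first clause reads "a 95% confidence interval will extend +/- 0.769 standard deviation if there are 8 patients in the active group". The rest of the sentence gives half-widths of "0.635 if the sample size is 12 and +/- 0.554 SDs if the sample size is 15". No formula is named. Only the first clause mentions the active group; the other two refer to a sample size without saying whose.

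Section 5.1 states that "The primary outcome will be feasibility".

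**The concern.** The three pairs of sample size and half-width stand in one sentence and should come from one formula. Two of them do, and the first does not. A reader who takes the 8-patient case as the poor-retention scenario for the active arm would therefore either rely on an interval that is too narrow or be looking at the wrong patient count.

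This is the plan's only statement of precision for the continuous outcomes, and the pilot is meant to supply means and variability for designing a later trial. That is a reason to have the figure right, although nothing in this study is decided by it.

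**Working it through.** **Inputs, all from Section 6.0**

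- Confidence level 95%, read as two-sided because the figures are given as plus or minus.
- Stated pairs: n = 8 with 0.769 SD; n = 12 with 0.635 SD; n = 15 with 0.554 SD.
- Planned arms: 14 in PAI and 7 in HLI.

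**Step 1: identify the formula.** The half-width of a t interval for a single mean, in SD units, is

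h(n) = t(0.975, n−1) / √n.

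| n | t(0.975, n−1) | h(n) | Stated |
|---|---|---|---|
| 8 | 2.3646 | 0.8360 | 0.769 |
| 9 | 2.3060 | 0.7687 | not given |
| 12 | 2.2010 | 0.6354 | 0.635 |
| 14 | 2.1604 | 0.5774 | not given |
| 15 | 2.1448 | 0.5538 | 0.554 |

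The values for 12 and 15 reproduce to three decimals, which fixes the formula. The value for 8 does not reproduce. The printed 0.769 is the n = 9 result after rounding.

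**Step 2: look for another reading that gives 0.769 at n = 8.**

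- Normal quantile: 1.96/√8 = 0.693.
- Multiplier of 2: 2/√8 = 0.707.
- One-sided 95% t quantile: 0.670.
- Division by √(n−1) instead of √n: 0.894.
- Other degrees of freedom with √8: 6 df gives 0.865, 8 df 0.815, 10 df 0.788, 11 df 0.778, 12 df 0.7703 and 13 df 0.7638. The half-width falls steadily as the degrees of freedom rise and passes 0.769 between 12 and 13, so no whole number of degrees of freedom rounds to it.
- Two-sample difference with 8 in the active arm: 1.072 (8 against 8), 1.118 (8 against 7), 1.364 (8 against 4).

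None gives 0.769. An alternative would also have to keep 0.635 at 12 and 0.554 at 15.

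**Step 3: size of the discrepancy if 8 is the intended count.**

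- Difference: 0.836 − 0.769 = 0.067 SD.
- Relative to the correct value: 0.769/0.8360 − 1 = −8.0%.
- Coverage of ±0.769 SD at n = 8: 2·F(0.769 × √8) − 1 = 2·F(2.175) − 1 = 0.934, where F is the t distribution function with 7 df.

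If 0.769 is the intended half-width, the count should be 9 and the precision itself is correct.

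**Step 4: the sample sizes 12 and 15.** Both half-widths are correct for the sizes given. If these clauses also mean the active group, 15 is more than the 14 planned for PAI, and the planned size is missing from the list. The half-width at 14 is 0.577 SD, so the figure for 15 is 0.5774 − 0.5538 = 0.024 SD smaller (0.5538/0.5774 − 1 = −4.1%). If the clauses mean all patients, 15 of 21 is possible and nothing is out of range.

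**The case against.** The arithmetic is not open to dispute; the objections concern weight.

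First, the sentence only illustrates precision at hypothetical sizes. The continuous outcomes are to be summarised descriptively, no threshold or test uses 0.769, and 8 is not the planned size of the active arm. This stands, and it keeps the point minor.

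Second, a single digit, 8 written for 9, would explain everything. In that case the stated precision is right, and the 8.0% and 93.4% figures do not apply. This also stands as a possibility, so those two figures are conditional on 8 being intended. It does not remove the error, because the pair as printed is wrong on either reading. A misread digit in the text taken from the PDF cannot be strictly excluded, but the surrounding digits are clean and nothing points to one.

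Third, the remark about 15 against 14 is not an error in the plan. A planning list may include a size just above the target, and the clause may not mean the active group at all. This is accepted: 0.554 is correct for 15, and only a clarification is asked for.

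Finally, this is one sentence in a section whose other precision statement also needs checking. The interval from 0.211 to 0.789 given just before it for 21 patients is the Clopper-Pearson interval for 6 of 12. That is a separate matter and is not relied on here.

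**Conclusion.** The point holds. The stated half-width and the stated number of patients in the first clause do not belong together: 8 patients give ±0.836 SD, and ±0.769 SD belongs to 9. The documents do not settle which number slipped.

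The conclusion assumes a two-sided t interval for a single mean. The plan does not name this, but the other two figures in the sentence confirm it.

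Severity is minor. The primary outcome, the enrolment target and every planned analysis are unaffected.

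**What to change.** Confirm which number was intended and restate the first clause of the sentence in Section 6.0 as either ±0.836 SD with 8 patients or ±0.769 SD with 9.

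Leave the half-widths for 12 and 15 as they are, but say which group each sample size refers to. If it is the active group, it would help to give ±0.577 SD for the planned 14, either in place of the figure for 15 or beside it. That part is a clarification, not a correction.

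The cost is one sentence of editing. No analysis, enrolment number or decision changes.

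### The precision figures for continuous outcomes in Section 6.0 do not match the planned 14 + 7 patients: the largest size shown (15) exceeds the active arm, and the figure for 8 patients belongs to 9

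*Combined protocol and SAP*

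**What the plan says.** Section 6.0 (Analytic Plan) opens with the allocation: "We will enroll 21 patients with 14 in the PAI and 7 in HLI". Under Feasibility it says that "for the patients receiving the active intervention we will assess the change in outcomes of interest to determine preliminary efficacy estimates", and adds: "The control patients will also provide some preliminary efficacy assessments".

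Two precision statements follow. The first concerns the proportion of patients with measurements. It describes an exact 95% Clopper-Pearson interval for 21 patients "with a width of 0.578 (i.e., from 0.211 to 0.789 if the observed proportion is 0.5". The second concerns the outcomes of interest: "a 95% confidence interval will extend +/- 0.769 standard deviation if there are 8 patients in the active group", then ±"0.635 if the sample size is 12" and finally ±"0.554 SDs if the sample size is 15".

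The section gives no figure for 14 patients and none for 7. It states no dropout rate and does not name the formula behind the half-widths.

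**The concern.** The second statement is the only one in the plan on the precision of the continuous outcomes, and those estimates are meant to inform the design of a later trial. A reader would expect it to include the planned active-group size, with smaller sizes to show the effect of attrition. Instead it omits 14 and ends at 15, a size the planned arm does not have. Smaller sizes can stand for missing data; a larger one cannot.

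That raises the question whether the other figures were calculated for this design. If they were not, someone using the section to plan the next study would take precision values that do not belong to the sample sizes printed beside them.

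**Working it through.** **Inputs, all from Section 6.0:** allocation 21 = 14 PAI + 7 HLI; confidence level 95%; half-widths of 0.769, 0.635 and 0.554 SD at sizes 8, 12 and 15; exact interval 0.211 to 0.789 (width 0.578) attributed to 21 patients at an observed proportion of 0.5.

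**Step 1: identify the plan's formula.** A two-sided 95% t interval for one mean has half-width, in SD units, t(0.975, n−1)/√n.

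- n = 15: 2.145/3.873 = 0.554. Matches the plan.
- n = 12: 2.201/3.464 = 0.635. Matches the plan.

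A normal-quantile interval would give 0.506 at n = 15 and 0.566 at n = 12, so it is not what was used.

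**Step 2: apply the same formula to the remaining sizes.**

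| n | t(0.975, n−1)/√n | Half-width (SD) | Plan states |
|---|---|---|---|
| 15 | 2.145/3.873 | 0.554 | 0.554 |
| 14 (planned PAI) | 2.160/3.742 | 0.577 | not given |
| 12 | 2.201/3.464 | 0.635 | 0.635 |
| 9 | 2.306/3.000 | 0.769 | not given |
| 8 | 2.365/2.828 | 0.836 | 0.769 |
| 7 (planned HLI) | 2.447/2.646 | 0.925 | not given |

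- 15 versus 14: 0.577/0.554 = 1.04, so the half-width at the planned size is about 4% wider. On unrounded values (0.5774 − 0.5538) the difference is 0.024 SD.
- 8 patients: the printed 0.769 is the n = 9 value. 0.769/0.836 = 0.92, so the printed half-width is about 8% too narrow for its stated size.

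**Step 3: the neighbouring exact interval.** The Clopper-Pearson limits for x of n are the 0.025 quantile of Beta(x, n−x+1) and the 0.975 quantile of Beta(x+1, n−x).

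- 6 of 12: 0.211 to 0.789, width 0.578. This is the interval the plan prints.
- 10 of 21: 0.257 to 0.702, width 0.445.
- 11 of 21: 0.298 to 0.743, width 0.445.

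An observed proportion of exactly 0.5 is not possible with 21 patients, so 10 and 11 of 21 are the nearest cases. The printed width is the one for 12 patients, and 0.578/0.445 = 1.30, about 30% wider than 21 patients would give. This error understates the precision, whereas the n = 8 error overstates it.

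**The case against.** The strongest defence is that the sentence is a conditional grid. It says what the half-width would be if the size were 8, 12 or 15, and nowhere claims that the trial will achieve ±0.554 SD. The planned-size value, 0.577, lies between the printed values for 12 and 15, so a reader is not misled about the order of precision. This stands. A reader might infer that the plan promises a precision it cannot reach, but the text makes no such promise.

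Second, the words tying the figures to the active group are attached only to the size of 8; the sizes 12 and 15 are simply called sample sizes. The next paragraph describes descriptive statistics on all enrolled patients, and 15 measured out of 21 is possible. So the documents do not show that 15 could never occur on any reading. The active-group reading is still the natural one: the sentence runs on from that group, the efficacy paragraph before it concerns that group, and no pooled efficacy estimate is described. If pooling was intended, the sentence needs to say so.

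Third, nothing depends on the 4%. The primary outcome in Section 5.1 is feasibility, the continuous outcomes receive descriptive statistics, and no test, threshold or sample-size choice is linked to ±0.554 SD. This also stands.

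Fourth, the absence of a control-arm figure is missing detail, not a miscalculation. It is tempting to say that control-arm precision is 67% worse than stated (0.925/0.554 = 1.67), but that sets 7 controls against 15 active patients, and the plan states no control-arm figure from which to depart.

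None of these arguments rescues ±0.769 SD for 8 patients, which is wrong at its own stated size, or the exact interval attributed to 21 patients.

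**Conclusion.** The point holds as a correction to the precision text. On the natural reading, the most favourable half-width is given for an active group one larger than the 14 planned; the planned size gives ±0.577 SD, a minor change. The figure for 8 patients is an arithmetic error: it should be ±0.836 SD, so the printed value is about 8% too narrow. The companion exact interval is the one for 6 of 12, and its width with 21 patients should be about 0.445.

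This rests on two assumptions: that the half-widths are two-sided 95% t intervals for one mean, which the exact matches at 12 and 15 support, and that 12 and 15 are active-group sizes, which is the natural but not the only reading. The n = 8 correction depends only on the first. The exact-interval correction depends on neither, because the plan names the method and the sample size.

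The documents do not support any inference that the design is unsound or that a conclusion of the trial is at risk.

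**What to change.** Replace the half-width sentence in Section 6.0 with one calculated for the planned arm and for plausible attrition: *±0.577 SD if all 14 PAI patients are measured, ±0.635 SD if 12 are measured and ±0.836 SD if 8 are measured.* For completeness, ±0.925 SD for the 7 HLI patients may be added. Changing only the entry for 15 would leave the wrong figure for 8 in the same sentence.

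In the same edit, correct the Clopper-Pearson sentence: with 21 patients the width near 0.5 is about 0.445, for example 0.257 to 0.702 if 10 of 21 have the measurement.

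The cost is a rewording of two sentences, with no change to design, conduct or data collection. The stated precision for the continuous outcomes becomes slightly less favourable; that for the proportions becomes more favourable.

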7.0 Data Management

Informed consent document	WISER/OnCore/PIC/[name] Research Server/Research Chart
Protocol registration form	ORIS/[name] Research Server/Research Chart
Quality of Life Questionnaires	REDCap
MRI and CPET data	[name] Research Server
Self-Efficacy for Walking	REDCap
FACT-Lym	REDCap
Neuro-Cognitive Measures	REDCap

8.0 Confidentiality and Privacy

Confidentiality will be protected by collecting only information needed to assess study outcomes, minimizing to the fullest extent possible the collection of any information that could directly identify subjects, and maintaining all study information in a secure manner. To help ensure subject privacy and confidentiality, only a unique study identifier will appear on the data collection form. Any collected patient identifying information corresponding to the unique study identifier will be maintained on a linkage file, stored separately from the data. The linkage file will be kept secure, with access limited to designated study personnel. Following data collection subject identifying information will be destroyed (state the anticipated time the data will be destroyed, e.g. three years after closure of the study, and the method of destruction), consistent with data validation and study design, producing an anonymous analytical data set. Data access will be limited to study staff. Data and records will be kept locked and secured, with any computer data password protected. No reference to any individual participant will appear in reports, presentations, or publications that may arise from the study.

Improving Exercise Capacity with a Tailored Physical Activity Intervention in Lymphoma and Breast Cancer Patients Undergoing Treatment – An addendum to NIH
R01CA167821 “Early Imaging Detection of CV Injury after Cancer”
Wake Forest Baptist Comprehensive Cancer Center
CCWFU# 99112

9.0 Data Safety and Monitoring

The principal investigator will be responsible for the overall monitoring of the data and safety of study participants. The principal investigator will be assisted by other members of the study staff.

Appendix A – Protocol Registration Form

DEMOGRAPHICS

Patient: Last Name: _____ First Name: _____

MRN: _____ DOB (mm/dd/yy): _____ / _____ / _____

ZIPCODE: _____

SEX: Male Female Ethnicity (choose one): Hispanic
 Non-Hispanic

Race (choose all that apply) WHITE BLACK ASIAN

apply): PACIFIC ISLANDER NATIVE AMERICAN

Height: _____ inches

Weight: _____ lbs. (actual)

Surface Area: _____ m²

Primary Diagnosis: _____

Date of Diagnosis: ____ / ____ / ____

Performance Status: _____ ECOG Karnofsky

PROTOCOL INFORMATION

Date of Registration: _____ / _____ / _____

MD Name (last) : _____

Date protocol treatment started: _____ / _____ / _____

Informed written consent: YES NO

(consent must be signed prior to registration)

Date Consent Signed: _____ / _____ / _____

PID # (to be assigned by ORIS): _____

Protocol Registrar can be contact by calling [contact] between 8:30 AM and 4:00 PM, Monday – Friday.

Completed Eligibility Checklist and Protocol Registration Form must be hand delivered, faxed or e-mailed to the registrar at [name] or [contact].

Appendix B – Subject Eligibility Checklist

IRB Protocol No.	CCCWFU Protocol No.
Study Title: Improving Exercise Capacity with a Tailored Physical Activity Intervention in Lymphoma and Breast Cancer Patients Undergoing Treatment – An addendum to NIH R01CA167821 “Early Imaging Detection of CV Injury after Cancer”	
Principal Investigator: Dr. [name]	

Inclusion Criteria (as outlined in study protocol)	Criteria is met	Criteria is NOT met	Source Used to Confirm * (Please document dates and lab results)
Male or Female			WakeOne
Aged 18-85 years			WakeOne
Stage I-IV Lymphoma (Hodgkin or non-Hodgkin) or stage I-IV breast cancer			WakeOne
Expect to receive an anthracycline based chemotherapeutic regimen or other potentially cardiotoxic cancer therapies			WakeOne
Capacity to walk at least 2 city blocks on a flat surface			WakeOne
Expected survival beyond 6 months			WakeOne
Exclusion Criteria (as outlined in study protocol)	Criteria NOT present	Criteria is present	Source Used to Confirm * (Please document dates and lab results)
Contraindication for MRI			WakeOne
Contraindications for exercise training or testing			WakeOne
Inability to exercise on treadmill or stationary cycle			WakeOne
Claustrophobia			WakeOne
Unstable angina			WakeOne
Pregnant			WakeOne
Inability to provide informed consent			WakeOne

This subject is eligible / ineligible for participation in this study.
 ORIS Assigned PID: _____

Improving Exercise Capacity with a Tailored Physical Activity Intervention in Lymphoma
and Breast Cancer Patients Undergoing Treatment – An addendum to NIH
R01CA167821 “Early Imaging Detection of CV Injury after Cancer”
Comprehensive Cancer Center of Wake Forest University (CCCWFU- #99112)

Signature of research professional confirming eligibility: _____

Date: ____ / ____ / ____

Signature of Principal Investigator confirming eligibility: _____

Date: ____ / ____ / ____

* Examples of source documents include clinic note, pathology report, laboratory results, etc. When listing the source, specifically state which document in the medical record was used to assess eligibility. Also include the date on the document. Example: “Pathology report, 01/01/14” or “Clinic note, 01/01/14”

APPENDIX C: MRI-CPET Protocol and Encounter Form

CPET Stress Cardiovascular MRI Procedure Guidelines

Non-Contrast Exam

Abbreviations:

BH: Breath hold

CMRI: Cardiovascular magnetic resonance imaging

CPET: Cardio-Pulmonary Exercise Test

ECG: Electrocardiography

GRE: Gradient recalled echo

LAO: Left anterior oblique

IR: Inversion recovery

NBH: Non breath hold

PSIR: Phase sensitive inversion recovery

SSFP: Steady state free precession

TSE: Turbo spin echo

VLA: Ventricular long axis

Study image and completion form transfer note to MRI Technologist:

Improving Exercise Capacity with a Tailored Physical Activity Intervention in Lymphoma and Breast Cancer Patients Undergoing Treatment – An addendum to NIH R01CA167821 “Early Imaging Detection of CV Injury after Cancer”
Comprehensive Cancer Center of Wake Forest University (CCCWFU- #99112)

Immediately upon completion of the study, technologists should submit images to the MRI Reading Center at Wake Forest via the CTP node on the scanner. From that PC, participants' images will be automatically encrypted and transmitted to the MRI core lab for further analysis. The encryption schema used is https, the standard for secure website transactions, used by banks and e-commerce worldwide. Additionally, technologists should burn a CD to give to the Study Coordinator for secured storage. Data should also be stored on the local PACS system. MRI technologists should fill-out the MRI completion form and give to the Study Coordinator for transmission to the MRI Reading Center.

